1 ABBREVIATIONS AND GLOSSARY

1.1 Abbreviations

Abbreviation	Definition
ACALES	Adaptive Categorical Listening Effort Scaling
ADE	Adverse Device Effect
AE	Adverse Event
ASC	Automatic Scene Classifier
ASM	Automatic Sound Management
APSQ	Audio Processor Satisfaction Questionnaire
CI	Cochlear Implant
CIP	Clinical Investigation Plan
CRF	Case Report Form
DD	Device Deficiency
FEP	Front-end Processing
HISQUI	Hearing Implant Sound Quality Index
IB	Investigator Brochure
ICF	Informed Consent Form
IEC	Independent Ethics Committee
ISF	Investigator Site File

OLSA	Oldenburger Sentence Test (Oldenburger Satztest)
NR	Noise Reduction
PI	Principal Investigator
SADE	Serious Adverse Device Effect
SAE	Serious Adverse Event
SNR	Signal-to-Noise Ratio
SOP	Standard Operating Procedure
SRT	Speech Reception Threshold
SSQ12	The Speech, Spatial and Qualities of Hearing Scale (short version with 12 questions)
TMF	Trial Master File
TR	Transient Noise Reduction
USADE	Unanticipated Serious Adverse Device Effect
WNR	Wind Noise Reduction

Confidential

CIP Version: 1.2

[figure not shown]
[figure not shown]
Template version: 3.0

Clinical Investigation Plan
FEP3, [REDACTED]

09 May 2019

Page 12 of 75

Confidential

CIP Version: 1.2

Template version: 3.0

Clinical Investigation Plan
FEP3, [REDACTED]
09 May 2019

Page 13 of 75

Confidential

CIP Version: 1.2

Template version: 3.0

Clinical Investigation Plan
FEP3, [REDACTED]
09 May 2019

Page 14 of 75

Test interval	Test Condition	Test performed
First visit (upgrade)	SONNET (must be the current audio processor)	Speech tests in quiet (Freiburg Monosyllables)
		Questionnaires
	SONNET 2	
 • Fitting of all audio processor configurations • Speech test in quiet in all 6 configurations • Subject sent home with two configurations (randomised across subjects)
		Note: the subjects' SONNET stays at the clinic until the study is completed (or subject is withdrawn)
Second visit	SONNET	Speech tests in noise (S0N0)
	SONNET 2	
 • Readout and save data logging

		
 • Questionnaires • Speech tests in noise (S0N0) in all 6 configurations • Speech tests in noise (S0N0T0) in the SONNET configuration and SONNET 2 configuration 1 and 2
		
 • Subject send home with two configurations (randomised across subjects)
Third visit	SONNET	Speech tests in noise with 5 loudspeakers (S0, $\pm N45$, $\pm N135$)
	SONNET 2	
 • Readout and save data logging
		
 • Questionnaires • Speech tests in noise 5 loudspeakers (S0, $\pm N45$, $\pm N135$) in all 6 configurations
		
 • Subject send home with two configurations (randomised across subjects)
Fourth visit	SONNET 2	
 • Readout and save datalogging
		
 • Questionnaires • Subjective ratings
		
 • Subject send home with two configurations (randomized across subjects)
Fifth visit	SONNET 2	Readout and save datalogging (
		Subjective ratings
		Give back the subject's SONNET

Table 1. Study overview

3 INTRODUCTION

3.1 Literature Review

Cochlear implant (CI) users have experienced a steady improvement in their speech perception scores through the last decades (Zeng, 2004; Zeng, Rebscher, Harrison, Sun, & Feng, 2008). Nowadays, many CI users perform at ceiling in sentence tests in quiet (i.e. > 90%), and many CI users successfully converse over the telephone (Zeng, 2004; Zeng et al., 2008). Although the introduction of fine structure coding strategies and bi-directional microphones have improved the hearing performance in more challenging listening conditions, CI users still face considerable challenges when listening in background noise, reverberating surroundings (Cacace, Kleine, Holt, & Dijk, 2016; Finke, Strauss-Schier, Kludt, Buchner, & Illg, 2017).

In contrast to normal hearing people, cochlear implant users typically need a signal-to-noise ratio (SNR) of at least +5 dB, but often up to +20 dB to reach a 50% speech reception threshold (SRT) (Nelson, Jin, Carney, & Nelson, 2003; Stickney, Zeng, Litovsky, & Assmann, 2004; Zeng et al., 2008). Importantly, CI users' speech reception scores in noise often drop remarkable compared their scores in quiet (Finke et al., 2017; Schafer & Thibodeau, 2004; Wolfe & Schafer, 2008) which may lead to a considerable increase in listening effort and a loss in quality of hearing. CI users tend to have even more difficulties speech understanding if exposed to fluctuating noise (e.g. slamming doors, clattering dishes) than in stationary noise or noise with relatively low temporal variations (e.g. car engine) (Fu & Shannon, 1999; Nelson et al., 2003; Stickney et al., 2004; Zeng & Galvin, 1999). Therefore, the improvement of speech understanding in noise is still a very important topic in the CI field.

Early CI development aiming at enhancing speech recognition, have focused on increasing number of channels and the stimulation rate and improving the signal-processing strategies and the electrode design. Considerable improvements were also reached by improved front-end processing methods. MED-EL cochlear implants incorporate the Automatic Sound Management (ASM). This technology provides a wide input dynamic range and to some extent protection from sudden loud sound to cochlear implant users which is achieved by a dual loop automatic volume control and automatic gain control. Additionally, dual, omni-directional or adaptive directional microphones, and remote microphone technologies can improve signal quality by optimizing the acoustic signal. In combination with pre-processing algorithms, the signal can be enhanced for different environments, for instance by automatically identifying sounds, and thus customized for the individual user. A common approach is to use two omni-directional microphones to form fixed or adaptive directional microphones, also known as beamforming. With the SONNET, MED-EL introduced ASM 2.0 including wind-noise reduction and microphone directionality and significant improvements in speech performance could be shown (Hagen et al., In submission). With the most recent audio processor, SONNET 2, ASM 3.0 including new front-end features were incorporated: the noise reduction, the transient noise reduction and an automatic scene classifier.

3.2 Previous Clinical Experience

[figure not shown]
The SONNET 2 is an approved medical device indicated for individuals suffering severe to profound hearing loss. This study is designed to test speech perception quiet and in noise using different front-end processing features and collect subjective feedback on these new features by the use of different questionnaires (details are described in Section 10.2). Detailed information on the device can be found in Section 4.

[figure not shown]
3.3 Rationale

Similar to previous studies on audio processor and software development, this study investigates the new front-end features incorporated in the most recent audio processor SONNET 2.

[figure not shown]
This study is planned as an active post-market follow-up with an approved product bearing a CE mark, within its intended use.

[figure not shown]
Subjects will undergo the study-specific speech in quiet and speech in noise test and will complete questionnaires. This design will allow to a direct comparison of objective and subjective measures to test the new front-end features.

4 INVESTIGATIONAL DEVICE DESCRIPTION

4.2 Storage

[figure not shown]
[figure not shown]
[figure not shown]
SONNET 2 audio-processor will be stored at the clinic according to the provision of the User Manual (see Section 21.1, Appendix 1 for details). The previous SONNET audio-processor will be stored at the clinics under the responsibility of the Investigator. An accountability log will be set-up to track the subjects' devices.

4.3 Accountability Procedures

Subjects will receive a SONNET 2 for the duration of the study. The audio processor will be handed over at the first study visit. To control for the SONNET 2 use during the study, the subject's audio processor will remain in the centre during active study participation and will be given back after completing the study (see section 4.2 for details regarding the SONNET audio-processor retaining and storage procedure). If the subject discontinues the study for any reasons, the subject will get back their own audio processor in the original setting (I.e. SONNET) without unnecessary delay. Might re-fitting be required the procedure

will be implemented according to the centre clinical routine procedures for follow up fitting. The details of the procedure will not be recorded as part of the study.

After study completion (all visits attended) the participants have the choice to keep the SONNET 2 processor or return it. The choice will be recorded during the last visit and will be descriptively analysed as study outcome.

4.6 Study population

This study aims to enrol experienced adult users of the MED-EL cochlear implant system.

- **Target population:** adults of both sexes suffering from sensorineural hearing loss as specified in the SONNET 2 Intended Use (IU) in the User Manual (See Section 21.1, Appendix 1 for details)
- **Accessible population:** target population matching all inclusion and exclusion criteria as defined in section 8.1
- **Intended population:** accessible population that can be recruited by the study site appointed for this study
- **Actual population:** intended population enrolled in the study without considering drop-out or withdrawal
- **Analytic population:** actual population meeting all criteria for analysis

the study population is identified with the analytic population.

4.7 Study Procedures

This study is performed in experienced adult users of the MED-EL Cochlear Implant System and involves an upgrade of the audio processor. Additionally, speech tests and questionnaires outside the clinical routine will be implemented.

For a detailed description of all study procedures, see Section 11.

4.8 Fitting

This study will involve fitting sessions in order to set the maps with the various configurations of front-end processing available for the SONNET 2.

Fitting will generally follow the clinical practice at the centre. Particular front-end features will be enabled/disabled for the four configurations.

Table 2 Overview of the different SONNET 2 fitting configurations

Audio Processor	Configuration	ASC	WNR	Beam-former	AGC Compression	AGC Sensitivity	NR	TR
SONNET	Default	N/A	Mild	NAT	3:1	75%	N/A	N/A
SONNET 2	OPUS 2	Off	Off	OMNI	3:1	75%	N/A	N/A
SONNET 2	SONNET (default)	Off	Mild	NAT	3:1	75%	N/A	N/A
SONNET 2	SONNET 2/1	Off	Mild	NAT	3:1	75%	Mild	Mild
SONNET 2	SONNET 2/2	Off	Mild	NAT	3:1	75%	Strong	Strong
SONNET 2	SONNET 2/3	Mild	Mild	Auto (NAT)	3:1	75%	Auto (Off-Mild)	Auto (Off-Mild)
SONNET 2	SONNET 2/4	Strong	Strong	Auto (OMNI-ABF)	3:1	75%	Auto (Off-Strong)	Auto (Off-Strong)

4.9 Permitted Concomitant Treatments

Medications that are considered necessary for the subject's welfare and are not specifically prohibited may be given at the discretion of the Investigator.

5 STUDY OBJECTIVES

5.1 Primary Objectives

Comparison between the speech reception thresholds in the OLSA test in noise (S0N0) of the SONNET 2 programmed as a SONNET and the SONNET 2 (setting 1; ASC off, mild WNR, mild NR, mild TR).

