6 HYPOTHESES

6.1 Hypotheses for the Primary Objectives

The primary objective of this study is to show non-inferiority of SONNET2 in a OLSA in noise speech test (S0N0) compared to the SONNET. The margin of non-inferiority is set to 2 dB SNR (Hey, Hocke, Hedderich, & Müller-Deile, 2014; Nogueira, Rode, & Buchner, 2016).

- Verbal formulation

Hypothesis H_0 (Null Hypothesis):

Speech perception with the SONNET 2 in its default setting in the OLSA in noise (S0N0) is inferior to the speech perception in the same test condition with the SONNET.

Hypothesis H_1 (Alternative Hypothesis):

Speech perception with the SONNET 2 in its default setting in the OLSA in noise (S0N0) is non-inferior to the speech perception in the same test condition with the SONNET.

- Mathematical formulation

$$H_0: \mu_1 - \mu_2 \geq \Delta \text{ (2 dB SNR)}$$

$$H_1: \mu_1 - \mu_2 < \Delta \text{ (2 dB SNR)}$$

Where:

μ_1 = SONNET mean OLSA in noise (S0N0) results for the study population expressed in dB SNR

μ_2 = SONNET2 mean OLSA in noise (S0N0) results for the study population expressed in dB SNR

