7 STUDY DESIGN

7.1 Type of Study

This study has been planned as a mono-centric, open label, prospective longitudinal study where each subject acts as his/her own control.

The SONNET 2 is an incremental innovation to the SONNET audio processor with additional front-end processing features which are designed to improve patient performance in specific auditory environments. The study is designed to prospectively follow-up experienced SONNET users who received the SONNET 2. As intra-individual control, subjects will be acutely tested with the SONNET in the same test conditions as with the SONNET 2.

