7.3 Sample Size Calculation

The primary objective of this study is to show non-inferiority of SONNET2 in a OLSA in noise speech test (S0N0) compared to the SONNET. The margin of non-inferiority is set to 2 dB SNR (Hey et al., 2014; Nogueira et al., 2016).

Comparable data of the final report "Performance of Cochlear Implant Patients with Microphone Directionality and Wind Noise Reduction with the "SONNET" of the OLSA in noise speech test (S0N0) were used as basis for the sample size calculation (Hagen et al., In submission):

OPUS2	mean: 0.589 dB;	± SD: 1.586 dB vs.
SONNET natural-MILD	mean: -0.088 dB;	± SD: 1.463 dB

The sample size was estimated using the formula on noninferiority (Chow, Shao, & Wang, 2008):

$$N = (1 + \frac{1}{r})(\sigma \frac{Z_{crit} + Z_{pwr}}{(\mu_A - \mu_B) - \Delta})^2$$

Assuming a non-inferiority margin of 2 dB (Δ), with an alpha-level of 0.025 (noninferiority, one-sided) and a power of 90%, a minimum sample size of 13 subjects was calculated (Z_{crit} is the normal quantile for the 0.025 alpha level, and Z_{pwr} is the normal quantile for the 90%

power). To allow for possible dropouts (approximately 20%) and to provide additional safety and efficacy data, a maximum of 30 subjects will be included in this study.

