15 STATISTICAL ANALYSIS

15.1 Statistical Analysis Methods

Descriptive statistics will be calculated to report patients' baseline characteristics (e.g. age, gender) and to describe test outcomes. The mean, standard deviation (SD) and/or median with range (minimum and maximum) will be used to describe quantitative data; absolute and relative frequencies will be used to present qualitative data.

Inferential statistics: Data will be analysed based on the objectives and the formulated hypotheses described in sections 5 and 6. To choose whether a parametric or a non-parametric test shall be applied, the Kolmogorov-Smirnov test and a graphical examination will be used before to check the data distribution.

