15.1.1 Primary Objectives

A difference between SONNET2 in a OLSA in noise speech test (S0N0) and the SONNET shorter than 2 dB SNR (Δ) is not seen as a clinically relevant difference (Hey et al., 2014; Nogueira et al., 2016). A statistical significant difference will be examined applying Student's t-test or Wilcoxon signed-rank test.

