5 STUDY OBJECTIVES

5.1 Primary Objective

- Comparison between the speech reception thresholds in the OLSA test in noise (S0N0) of the SONNET 2 programmed as a SONNET and the SONNET 2 (setting 1; ASC off, mild WNR, mild NR, mild TR).

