11.2 Inferential Statistics

11.2.1 Primary Objectives

The mean difference (dB SNR) with the 95% confidence intervals of the OLSA in noise speech test (S0N0) between the SONNET and the SONNET2 will be calculated to examine if the mean difference lies below the a-priory specified non-inferiority margin of 2 dB.

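### The primary contrast is not the same in the objective and the hypotheses: three different SONNET versus SONNET 2 pairs could be tested against the 2 dB margin

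*Protocol*

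**What the plan says.** **Objective.** Protocol 5.1 defines the primary comparison as the S0N0 threshold "of the SONNET 2 programmed as a SONNET and the SONNET 2 (setting 1; ASC off, mild WNR, mild NR, mild TR". SAP 5.1 repeats it: "SONNET 2 programmed as a SONNET and the SONNET 2 (setting 1; ASC off, mild WNR, mild NR, mild TR".

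**Hypotheses.** The alternative in Protocol 6.1 begins "Speech perception with the SONNET 2 in its default setting in the OLSA in noise (S0N0) is non-inferior", and the comparator is the SONNET. SAP 9.1 uses the same formulation.

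**Sample size.** Protocol 7.3 refers to "non-inferiority of SONNET2 in a OLSA in noise speech test (S0N0) compared to the SONNET", and SAP 8 does the same. Neither names a configuration.

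**Primary analysis.** Protocol 15.1.1 speaks of "A difference between SONNET2 in a OLSA in noise speech test (S0N0) and the SONNET shorter than 2 dB SNR". SAP 11.2.1 calculates the mean difference and its confidence interval "of the OLSA in noise speech test (S0N0) between the SONNET and the SONNET2". Again no configuration is named.

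**Precedence.** Protocol 15.1 states: "Data will be analysed based on the objectives and the formulated hypotheses described in sections 5 and 6".

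**Control.** On the intra-individual control, Protocol 7.1 says that "subjects will be acutely tested with the SONNET in the same test conditions as with the SONNET 2". SAP 7.1 says the same.

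**The concern.** A non-inferiority test needs one reference condition and one test condition. Here the objective names a pair of programs on a single device, while the hypotheses name two devices and leave the SONNET 2 program open. These are different tests.

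A result on one device with and without noise reduction (NR) and transient noise reduction (TR) says nothing about the new hardware. A result for the patient's own SONNET against a SONNET 2 program mixes hardware with features, or tests hardware alone. Non-inferiority to the SONNET does not follow from the first, and a conclusion about features alone does not follow from the second.

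The study is open label and every candidate pair is measured at the same visit. If the text does not fix the pair, it could be fixed once the results are known. SAP 3 gives the avoidance of post hoc decisions as the purpose of the SAP.

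**Working it through.** **Step 1. Are the SONNET and the SONNET program on the SONNET 2 the same condition?** The documents treat them as distinct:
- Table 2 (Protocol 4.8) gives the SONNET processor one row and the SONNET 2 programmed as SONNET (default) another.
- The schedule in Protocol 9 also lists them on separate rows.
- At Visit 2, Protocol 9.2.1 tests the patient's SONNET in S0N0. Protocol 9.2.2 then tests the SONNET 2 in six configurations, including the SONNET set-up and setting 1.

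**Step 2. What is the SONNET 2's default setting?** No supplied section says. In Table 2 only one SONNET 2 row carries the label default, and it is the SONNET emulation, not setting 1.

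**Step 3. Which pairs are open?**

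| Reading | Reference | Test | What differs | Basis |
|---|---|---|---|---|
| (a) | SONNET 2 as SONNET | SONNET 2/1 | NR and TR only (not available vs mild) | Protocol 5.1, SAP 5.1 |
| (b) | Physical SONNET | SONNET 2/1 | Device plus NR and TR | Hypotheses, if default means setting 1 |
| (c) | Physical SONNET | SONNET 2 as SONNET | Device only | Hypotheses, if default means the Table 2 label |

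Reading (c) contradicts the objective and would test none of the new features.

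**Step 4. Does the sample size show which pair was meant?** Inputs from Protocol 7.3: SDs 1.586 and 1.463 dB, margin 2 dB, one-sided alpha 0.025, power 90%. Assumed, because not stated: r = 1, true difference 0, pooled SD.
- Pooled SD = √((1.586² + 1.463²)/2) = 1.526 dB.
- N = 2 × (1.526 × (1.960 + 1.282)/2)² = 12.23, rounded up to 13. The plan's figure is reproduced.
- The planning data compare OPUS2 with SONNET natural-MILD. That is none of (a), (b) or (c), so the 13 does not identify the pair.

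**Step 5. Illustration of size, for (a) and (b).** The documents give no within-subject correlation ρ and no SONNET versus SONNET 2-as-SONNET difference. Three conditions per patient were simulated with residual SD 1.526 × √(1 − ρ), ρ assumed from 0 to 0.8, and no hardware effect. Non-inferiority was declared if mean(d) + t(0.975, n−1) × SD(d)/√n < 2, where d is SONNET 2 setting 1 minus reference. The hypotheses as printed subtract the other way. The n = 24 case is 30 less 20% dropout.

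Share of trials in which (a) and (b) give opposite verdicts, at ρ = 0 / 0.3 / 0.5 / 0.8:

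| True difference | n = 13 | n = 24 |
|---|---|---|
| 0 dB | 0.178 / 0.072 / 0.016 / 0.000 | 0.016 / 0.001 / 0.000 / 0.000 |
| 1 dB worse | 0.315 / 0.346 / 0.340 / 0.105 | 0.332 / 0.271 / 0.173 / 0.004 |
| 2 dB worse | 0.042 / 0.043 / 0.042 / 0.042 | 0.041 / 0.041 / 0.041 / 0.042 |

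One-sided error if either pair may be claimed (ρ = 0.5, pair (a) exactly at 2 dB):
- Both pairs at 2 dB: 0.0461 at n = 13, 0.0455 at n = 24, 0.0459 at n = 30, against a nominal 0.025.
- n = 13, with setting 1 a further 0.1, 0.25 or 0.5 dB worse against the physical SONNET: 0.0368, 0.0295, 0.0258.

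**The case against.** The strongest defence is that Protocol 5.1 and SAP 5.1 are explicit and identical. The hypotheses are headed as belonging to the primary objective, so the SONNET there may be shorthand for the SONNET program. On this view the sections without a configuration are merely less specific, and the physical SONNET serves the secondary comparisons across all processors. It stands that the sample size and analysis sections do not themselves contradict the objective, and that Protocol 7.1 and SAP 7.1 describe the whole study and do not settle the primary comparator. The shorthand itself fails: no section states it, and Table 2, the schedule and Visit 2 all separate the two conditions.

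It is also fair that the default setting may be explained in text not supplied, or in the user manual that Appendix 1 only cites. The finding is therefore that the term is undefined in the supplied text. The conflict between sections is certain; the absence of any definition is not.

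A reader might infer that the sponsor will pick the pair after seeing results. The documents do not support that. They show only that the pair could be picked then, and the objective offers a natural default.

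A reader might also take the opposite-verdict rates of about one third as a forecast. They require an assumed 1 dB deficit that has no source in the documents. With no hardware effect assumed, they reflect only sampling noise between two reference measurements.

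**Conclusion.** The inconsistency is real and lies in the text of both documents. It does not depend on the simulation. The stated objective and the stated hypotheses are different tests, the sections that could settle the matter name no configuration, and Protocol 15.1 gives neither section precedence. Three readings are open, so it would be wrong to see only a choice between (a) and (b).

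The damage is mainly to interpretation: whichever pair is analysed, part of the plan's wording will not match the conclusion. The numerical effect is secondary and illustrative. One-sided error of about 4.6% instead of 2.5% is near the worst case. It needs selection between (a) and (b) after seeing the data, both pairs exactly at the margin, and no hardware effect. With ρ = 0.5 and n = 13, a further 0.5 dB deficit against the physical SONNET brings it to 2.6%. If the true difference is near 0 and ρ is at least 0.5, opposite verdicts occur in at most 1.6% of trials at n = 13.

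This should be corrected before analysis, because the two arms of the single confirmatory test are not fixed.

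**What to change.** Before analysis, name one reference and one test configuration by Table 2 row and visit, both in S0N0 at Visit 2. The choice is the sponsor's: (a) SONNET 2 programmed as SONNET (default) versus SONNET 2/1, or (b) physical SONNET versus SONNET 2/1. Reading (c) does not match the stated objective.

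- Use the chosen pair in Protocol 5.1, 6.1, 7.3 and 15.1.1 and in SAP 5.1, 8, 9.1 and 11.2.1.
- Replace the reference to the default setting with the named configuration.
- Word the primary conclusion to match: features on one device for (a), new device with setting 1 against the SONNET for (b).
- Report the other pairs as exploratory secondary comparisons, which Protocol 5.2 and SAP 5.2 already cover.

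The cost is a wording amendment to both documents. Under Protocol 7.6 it may need ethics committee notification or approval. No new testing is required, because all three conditions are already measured in S0N0 at Visit 2.
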